7.2.1 Study Schedule

Required Visit to CRC and blood draw	Time frame	CBC diff	Plasma DOH	NK and T cell flow cytometry	Pax geneRNA tube
#1, study visit, blood draw	Day 0	X	X	X	X
#2, study visit, blood draw	Day 1	X	X	X	X
#3, study visit, blood draw	Day 21	X	X	X	X
#4, study visit, blood draw	Day 35	X	X	X	X
#5, study visit, blood draw	Day 36	X	X	X	X
#6, study visit, blood draw	Day 56	X	X	X	X
#7, study visit, blood draw	Day 70	X	X	X	X

7.3 Duration of Participation

Each subject will remain in study for the duration of 70 days / 10 weeks

7.4 Test Article(s) (Study Drug(s) and/or Study Device(s))

7.4.1 Description

The commercially available dietary supplement Cogni.Q has been tested as in our completed PK study (See **Appendix 1**). Cogni.Q is sold as dietary supplement to promote cognitive agility and support healthy brain function, which are consistent with the reported neuro-protective

activities of AGN extract [11]. Cogni.Q and placebo capsules are provided by Cogni.Q manufacturer Quality of Life Labs (Purchase, NY, USA) (See letter of support, **Appendix 2**).

7.4.2 Treatment Regimen

Each subject will be instructed to take two capsules of Cogni.Q 200mg/Placebo by mouth twice daily for 21 days (Day 0 through Day 20) followed by a 14-day washout (day 21 through Day 34) and crossover to a second, 21-day treatment regimen (Day 35 through day 56). If they are assigned to group 1, participants will receive Cogni.Q 200mg on days 0 through 20 and a crossover to receive placebo on Days 21 through 34. If assigned to group 2, participants will receive placebo on Day 0 through 20 and crossover to receive Cogni.Q on Day 21 through 34.

7.4.3 Method for Assigning Subject to Treatment Groups

The statistician will generate a randomization table and provide to IDS.

7.4.4 Subject Compliance Monitoring

Study team members will text or give a reminder call to each subject to take the capsules weekly. On Day 21 and Day 56, study team will do a pill count for each subject of remaining number of capsules (to ensure that treatment regime was followed). Furthermore, plasma concentration of pyranocoumarins will be determined as compliance to AGN exposure.

7.4.5 Blinding of the Test Article

Cogni.Q and Placebo will be supplied to IDS at Penn State Hershey. IDS will be responsible for the storage, blinding, and dispensing of study medications.

7.4.6 Receiving, Storage, Dispensing and Return

7.4.6.1 Receipt of Test Article

Quality of Life will ship the Cogni.Q and Placebo capsules (cellulose) directly to IDS Pharmacy at Penn State Hershey Medical Center. An IDS staff member will inventory the shipment using the shipping invoice, notating lot number, expiration date, breakage, and total quantities. The shipment will be recorded on the study-specific drug accountability record.

7.4.6.2 Storage

The IDS Pharmacy will store the investigational product in the drug storage room within the IDS Pharmacy under the manufacturer's recommended storage conditions (room temperature). IDS Pharmacy utilizes a continuous, wireless, electronic temperature monitoring system. Temperature readings are monitored continuously and as long as no excursions occur, a recording is made every hour. Room temperature set-points are 20-25°C and the system is programmed to pre-alarm if the temperature reaches 21°C or 24°C. When temperatures reach a pre-alarm level, the system begins contacting the pharmacy personnel via phone and pager, 24 hours a day, 7 days a week. If the area reaches an alarm level, temperatures are recorded every 5 minutes or until the area is back within the acceptable range, whichever occurs first. The system continually calls and pages until someone acts on the alarm.

STORAGE/SECURITY: Access to the IDS Pharmacy (PG200) is limited to pharmacy personnel with badge swipe access and the drug storage room(PG200A) is locked with a key. The investigational product will be stored in a bin within the drug storage room and the bin will be clearly labeled with the name of the investigational product, the PI's name, and the IRB number to clearly differentiate the investigational product from other medications that are stored in the same area.

7.4.6.3 Preparation and Dispensing

IDS will maintain a bulk supply of Cogni.Q and a bulk supply of placebo for Cogni.Q capsules. The inventory for each supply will be tracked on corresponding drug accountability records.

IDS Pharmacy will receive a patient-specific prescription for the study material (i.e., Group 1 or Group 2, take 2 capsules by mouth twice daily as directed by the study team, Dispense Quantity: 84 capsules Refills: 1). NOTE: The IDS pharmacy will only dispense investigational products after receipt of the documents listed to ensure that the patient signed consent and is enrolled in the study.

RANDOMIZATION: A randomization list will be provided to IDS that includes subject numbers and a corresponding treatment regimen (Cogni.Q 1st /placebo 2nd or placebo 1st/Cogni.Q 2nd) so that they know what to dispense to each participant.

To ensure that the blind is maintained, the investigational product name will appear as “IDS Cogni.Q 200 mg or Placebo Capsules” on the pharmacy label.

After the IDS pharmacy receives the required documentation, the IDS pharmacy staff will prepare 84 capsules (21-day supply) of the product that a subject was randomized to. A subject-specific pharmacy label will be generated and affixed to the prescription vial.

A refill will be processed for the second dispensing after the washout period. No new prescription is required at this time because a refill was added to the initial prescription. The IDS Pharmacy staff will ensure that the randomization module is followed and the correct medication is dispensed for the second treatment period.

7.4.6.4 Return or Destruction of the Test Article

The participant will return their medication vial at the visits following their 21-day treatment periods. The participant return will be documented on the corresponding drug accountability record and the empty vial and any remaining capsules will be destroyed on-site as per the IDS Pharmacy’s destruction policy.

7.4.6.5 Prior and Concomitant Therapy

During the course of the study, prescription medicine and any medicine containing AGN are not permitted. At any point if a subject has to take prescription medication then they will be off the study.

8.0 Subject Numbers and Statistical Plan

8.1 Number of Subjects

40 healthy men

8.2 Sample size determination

We believe 20 participants in each group per arm in this 2 X 2 crossover design will allow us to detect an effect size of **0.75** (which is approximately equal to a difference of 920 in neutrophil mean count, assuming within-group common standard deviation is 1200, Table 2) between the two treatment arms with at least 81% power.

8.3 Statistical methods

Descriptive statistics and bivariate tests will be used to compare distributional properties of all measured variables within and between the Cogni.Q and placebo arms. The main outcome variables are

the neutrophil and NK count, which will be measured repeatedly. Linear mixed models will be used to analyze the study outcomes. More specifically, we will evaluate overall difference between the Cogni.Q and placebo arms (group effect), linear/nonlinear change over time (time effect), and group difference in this change (group-by-time interaction), separately for the pre- and post-crossover periods. We will then estimate the same model parameters but for the two crossover periods combined while controlling for potential carryover effect (i.e., group-by-period interaction). Our two-period crossover models will include the pre-crossover's baseline value (on Day 0) as a covariate common to the subsequent observations in both periods, thereby controlling for any carryover effect as well as bias due to difference at the first baseline. The outcome variables may be transformed to make sure the underlying statistical assumptions are satisfied. Other outcome variables including NK and neutrophil function assays will be analyzed in a similar statistical fashion. NK and neutrophil parameters will be examined for association for possible interaction/crosstalk. All analyses will be done using SAS version 9.4 or higher. The statistical significance level to be used is 0.05.

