1.0 Objectives

1.1 Study Objectives

The purpose of this pilot clinical trial is to test that daily intake of Korean *Angelica gigas* Nakai (AGN) dietary supplement (Cogni.Q, Quality of Life Laboratories, Purchase, NY) may boost human innate immune functions. Cogni. Q is a dietary supplement which is commercially available for anyone to purchase without a prescription for memory improvement.

The hypothesis to be tested is that daily consumption of Cogni. Q supplement leads to increased number and/or activation of neutrophils and Natural Killer (NK) cells in healthy men.

To test the hypothesis, we propose a double-blinded, placebo-controlled trial design (See scheme).

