1.2 Primary Study Endpoints

The primary endpoints/Aims are:

Primary Aim 1 (Tube 1). whole blood for CBC diff.

Primary Aim 2 (Tube 1). Flow analyses for NK cell counts.

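### Section 8.3 evaluates 12 overlapping treatment contrasts on neutrophil and NK counts at 0.05, and no section says which one decides the hypothesis

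*Combined protocol and SAP*

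**What the plan says.** Section 1.1 states the hypothesis as one sentence: daily Cogni.Q "leads to increased number and/or activation of neutrophils and Natural Killer (NK) cells in healthy men". Section 1.2 lists two primary aims, CBC with differential and "Primary Aim 2 (Tube 1). Flow analyses for NK cell counts", and names no contrast, visit or model for either.

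Section 8.3 takes as main outcomes "the neutrophil and NK count, which will be measured repeatedly". For these, "we will evaluate overall difference between the Cogni.Q and placebo arms (group effect"), together with a time effect and a group-by-time interaction. This is done "separately for the pre- and post-crossover periods. We will then estimate the same model parameters but for the two crossover periods combined", the latter "while controlling for potential carryover effect (i.e., group-by-period interaction"). The Day 0 value is a covariate. One level is given: "The statistical significance level to be used is 0.05". The section does not state sidedness, a multiplicity rule or a ranking of the analyses.

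Section 8.2 sizes the trial on a neutrophil difference "between the two treatment arms with at least 81% power" in a 2 x 2 crossover. It does not name the model, period or visit, and it does not cover NK count. Section 10.7 refers back to 8.3. Section 10.6 rules out an interim analysis, so repeated looks play no part.

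**The concern.** Three things combine. The hypothesis can be read as met by either cell type. Each cell type is examined by two treatment effects in three sets of data. All of these share one unadjusted level. Nothing in the plan fixes in advance which result answers the question, so the false-positive rate of the trial's conclusion is not defined.

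The combined model adds an ambiguity. If the group-by-period term is kept in it and the group effect is not explicitly averaged over periods, the reported contrast can amount to the period 1 comparison alone, which gives up the within-man comparison that the crossover was chosen for.

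This matters because the protocol expects to act on the answer. Section 2.3 speaks of positive data supporting immune enhancement, and section 12.2 of public benefit if efficacy results are positive. Section 3.0 says the findings will feed later trials. None of these sections defines positive.

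**Working it through.** **Step 1. Count the contrasts (8.3).** 2 outcomes x 2 treatment effects (group, group-by-time) x 3 data sets (period 1, period 2, combined) = 12, or 6 per outcome. Time effects, the carryover term, optional transformations and the function assays are left out of the count.

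**Step 2. The plan's own figure, 81% power (8.2).** Inputs: effect size 0.75, SD 1200, 20 men per group. 0.75 x 1200 = 900, whereas the stated difference is 920 (920/1200 = 0.767).
- Parallel two-sample t-test, two-sided 0.05: SE = 1200 x √(2/20) = 379.5, noncentrality 900/379.5 = 2.37, power 64%.
- Crossover, 40 men, one value per period, within-subject correlation r: SE = 1200 x √(2(1 − r)/40). At r = 0 this is 268.3, noncentrality 3.35, df 38, power 90%.

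A figure of 81% appears only with a correlation that the documents do not give, so it cannot be used to infer which contrast was intended. The error rates below do not depend on it.

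**Step 3. Bounds under independence.** At two-sided 0.05, a false increase has probability 0.025 per contrast.
- 12 contrasts: 1 − 0.975^12 = 26.2%.
- 6 contrasts: 1 − 0.975^6 = 14.1%.
- 2 contrasts: 1 − 0.975^2 = 4.9% for increases, and 1 − 0.95^2 = 9.75% in either direction.

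The 12 contrasts overlap, so the true figure for them is lower and needs simulation.

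**Step 4. Simulation with no effect.** The settings were 20 men per sequence, on-treatment visits on Days 1 and 21 and on Days 36 and 56, and two-sided 0.05. Two correlations had to be assumed.
- *Within-subject correlation:* ranged over 0.2 to 0.79. Table 2 in section 2.2 (paired p = 0.0004, SDs 1183 and 1396, n = 19, means 2065 and 2930) implies about 0.78, but over 24 hours only.
- *Neutrophil-NK correlation:* not in the documents; ranged over 0 to 0.9.

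| What may count | False increase | Either direction |
|---|---|---|
| Any of 12, ordinary readings of the models, outcome correlation up to 0.7 | 19-24% | 34-40% |
| Any of 12, same readings, outcome correlation 0.9 | 16-17% | 29-30% |
| Any of 12, combined contrast reduced to period 1, outcome correlation up to 0.7 | 15-19% | 28-33% |
| Any of 6, one outcome, all readings | 9-14% | about 22-23% (ordinary readings) |
| Combined group effect only, either outcome | 3-6% | 6-11% |

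The ranges cover different readings of the models as well as simulation error. For the last row, the independence values in step 3 (4.9% and 9.75%) are the natural reference.

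**Step 5. Cost of Holm across two outcomes.** The smaller p-value faces 0.025. With the crossover formula in step 2 and df 38:
- r = 0: noncentrality 3.35, power 90% falls to 84%.
- r = 0.5: SE 189.7, noncentrality 4.74, power 99.6% falls to 99.0%.

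**The case against.** The strongest reply is that the plan already points to one analysis. The design is a crossover, the sample size is for a between-arm neutrophil difference in that crossover, the overall group effect is listed first, and the combined model is where the description ends. On that reading the chance of a false increase across both outcomes is 3-6%, close to nominal, and the gap is a missing label. Section 8.3 also speaks of evaluating and estimating effects and does not list 12 confirmatory tests. The trial calls itself a pilot.

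Much of this stands. The combined group effect is the natural choice, and the 12-contrast family is a count of what the plan evaluates, not a decision rule that it states. What does not stand is that the label can be taken for granted. The text never gives it, and the group-by-period term leaves open what the combined effect would estimate. The pilot label does not settle it either, because section 2.3 sets out to establish the supplement's effect rigorously and sections 8.2 and 8.3 give power and a significance level.

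Two stronger readings are tempting and should not be drawn. A reader might infer that the investigators will claim success on any one of the 12 results; no section says so. A reader might also infer that, with a real effect of the planned size, the period 1, period 2 and combined neutrophil results would often disagree on significance. At a within-subject correlation of 0.79, next to the only value that the documents allow one to derive, this happens in about 2% of trials with two visits per period and 8% with one. Higher rates need correlations of 0 to 0.5, which are assumptions. Some disagreement is in any case expected when half the data are analysed alone.

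**Conclusion.** The point holds as a gap in pre-specification: 12 overlapping treatment contrasts, one level, an and/or hypothesis, and no named deciding contrast in 1.2, 8.2, 8.3 or 10.7.

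Its size is conditional. The 15-24% is the error rate that the wording leaves possible, not one that the plan commits to. It assumes that any significant increase could count, that tests are two-sided at 0.05 with only increases counted, and that the two assumed correlations lie in the ranges above. The range narrows to about 9-14% for one outcome and to 3-6% once the combined group effect alone decides. The conclusion does not turn on any particular correlation, because under the any-result rule the rate is well above nominal at every value tried.

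This should be corrected before unblinding. It does not invalidate the design.

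**What to change.** In sections 1.2 and 8.3:

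1. Name a single primary contrast for each of absolute neutrophil count and absolute NK count: the Cogni.Q-minus-placebo group effect from the combined two-period mixed model, averaged over both periods.
2. Examine carryover (group-by-period) in a sensitivity model, so that it cannot reduce the primary contrast to one period.
3. Label the period-specific models and all group-by-time terms supportive, reported with estimates and confidence intervals.
4. State one of two positions. Either the two aims are separate claims, each tested at two-sided 0.05 with no joint control, or one overall claim may rest on either outcome, in which case Holm is applied across the two.

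The cost is a text change, with no added subjects, visits or samples. Treating the aims as separate claims costs no power. Holm costs what step 5 of the working shows, a few percentage points at most, at the two within-subject correlations assumed there.

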9.0 Confidentiality, Privacy and Data Management

9.1 Confidentiality

See the Research Data Plan Review Form

9.1.1 Identifiers associated with data and/or specimens

See the Research Data Plan Review Form

9.1.1.1 Use of Codes, Master List

See the Research Data Plan Review Form

9.1.2 Storage of Data and/or Specimens

See the Research Data Plan Review Form

9.1.3 Access to Data and/or Specimens

See the Research Data Plan Review Form

9.1.4 Transferring Data and/or Specimens

See the Research Data Plan Review Form

9.2 Subject Privacy

See the Research Data Plan Review Form

10.0 Data and Safety Monitoring Plan

10.1 Periodic evaluation of data

The frequency of data review for this study differs according to the type of data and can be summarized in the following table (Table 10.1.1)

Table 10.1.1

Data type	Frequency of review	Reviewer
Subject accrual (including compliance with protocol enrollment criteria)	Quarterly	PI, Independent Monitor
Status of all enrolled subjects, as of date of reporting	Quarterly	PI, Independent Monitor
Adherence data regarding study visits and intervention	Quarterly	PI, Independent Monitor
AEs and rates (including out-of-range lab values)	Quarterly	Study physicians, PI, Independent Monitor
SAEs	Per occurrence	Study Physicians, PI, Independent Monitor, IRB

❖ Independent Monitor: [name]

❖ Study Physicians: [name], Ph. D, [name] and [name]

10.2 Data that are reviewed

Refer to Table 10.1.1 regarding who will be reviewing the data.

10.3 Method of collection of safety information

Subjects will be called weekly during the period when Cogni.Q or Placebo is given (Day 1 to Day 21 and Day 35 to 56) and reminded to take their capsules. They will be asked if they have experienced any of the expected AE (Anorexia, Nausea and Dyspepsia) or any unexpected AE that they have recorded in the medication diary.

If yes, study team personnel will inform the study physician(s) of the AE report. Study physician will contact the subject to assess the severity of AE and its relatedness to the intervention and record the data in Table 10.3.1. The physician(s) will take appropriate action of the care of the subject and make a decision in consultation with PI to whether keep the subject on the trial or withdraw.

Following table will be used to report and track any specific symptoms:

Table 10.3.1 AE reporting and tracking

Pt Identifier	AE Onset	AE End	Severity	SAE? (Y/N)	Relatedness	Action Taken	Outcome	Comments
Subj001	05/01/2019		1		2	1	4	Subject injured broke his hand
Subj002	06/26/2019		2		2	1	1	
Subj003	03/04/2019		3		0	4	4	Subj broke leg while skiing; withdrew from study

Severity of AE:

- 1 = Mild
- 2 = Moderate
- 3 = Severe
- 4 = Life threatening or disabling

Action Taken:

- 0 = None
- 1 = Medical intervention (specify in comments)
- 2 = Hospitalization
- 3 = Intervention discontinued
- 4 = Other

Relatedness to Intervention:

- 0 = Definitely unrelated
- 1 = Unlikely
- 2 = Possibly related
- 3 = Probably related
- 4 = Definitely related

Outcome:

- 1 = Resolved
- 2 = Recovered with minor sequelae
- 3 = Recovered with major sequelae
- 4 = Continuing treatment
- 5 = Condition worsening
- 6 = Patient death

Following table will be used to track subject status:

Table 10.3.2 Subject status

Pt Identifier	Date Enrolled	Date Completed Study	Study Status	Reason for Withdrawal
Subj001	03/02/2019	N/A	A	
Subj002	04/26/2019	9/20/2019	C	
Subj003	08/04/2019	N/A	W	Injury unrelated to intervention

Status:

- A = Active
- C = Completed
- W = Withdrew
- L = Lost to follow up

Following table will be used to keep track of the Frequency of specific symptom:

Table 10.3.3 Frequency of specific Symptoms

Symptoms	N%
Anorexia	
Nausea	
Dyspepsia	
Other	

10.4 Frequency of data collection

Data related to subject's safety will begin the day they are enrolled in the trial. Safety related information will be collect during the reminder calls, and by going over the medication diary maintained by the subject during their visit. Hence, the data related to subject's safety will be collected weekly and during their study visits to CRC.

10.5 Individuals reviewing the data

Refer to 10.1.1

10.6 Frequency of review of cumulative data

The PI, study biostatistician, study physicians and co-investigators will review the cumulative data. Cumulative data analysis will be done at the end of the trial (after the last subject has successfully completed the trial), since this the study subject number is less hence an interim analysis is not required.

10.7 Statistical tests

Study biostatistician will perform tests as described in 8.3. We do not see a need to perform statistics to determine safety because any occurrence will be evaluated immediately on a case-by-case basis.

10.8 Suspension of research

If any unexpected serious adverse events (SAE) occur, the research will be suspended and reports will be submitted to IRB for review and other regulatory office (FDA) as appropriate.

11.0 Risks

Physical health Risk assessment:

- Risk related to fasting:
 - Fasting for up to 8 hours could cause dizziness, headache, stomach discomfort, or fainting.
- Risk related to blood draw:
 - Blood draw needle pricks will inflict temporary superficial pain. Venipuncture might occasionally lead to localized hemorrhage and bruises at site of needle insertion. Our CRC experienced research nurses are highly trained and experienced which greatly reduces these risks. Occasionally, a subject may experience fainting spell during the blood draw. The CRC nurses are trained to respond to such situations. Subjects will be placed in a head-down position until consciousness is regained. Subjects will be monitored and given juice and/or light snacks until they are able to maintain blood pressure upon assuming an upright posture.
- Consumption of placebo vs Cogni.Q capsules:
 - As for the consumption of placebo vs. Cogni.Q capsules, we do not anticipate any more frequent or greater risks to the subject than the risks ordinarily encountered in daily life by taking a dietary supplement. Reported side effects for Cogni. Q include anorexia (lack of appetite), nausea and indigestion [12].
- Psychological, financial, legal risk assessment:
 - We do not anticipate any increased risk in these categories by participating in this study. Psychological reward might be a positive factor of participating in our study as most people derive pleasure by knowing study results may benefit themselves and many others. Financial loss due to missed work is partially mitigated by our subject remuneration plan (\$25 per visit).
 - Loss of confidentiality is a potential risk when conducting human subject research and hence, all efforts will be made by the study team to ensure that loss of confidentiality does not occur.

